#### 1.6.2 Intended Benefit for Subjects

This is a proof of concept study for the purpose of evaluating safety and efficacy of PRO 140 for further clinical testing in acute GVHD indication. The most significant limitation with the current GVHD prophylaxis treatments has been the necessity and challenge of continued adherence to the medications, along with relatively high risk of occurring GVHD. This study provides opportunity to the subjects to have supervised SC treatments with PRO 140 as an add-on to their current GVHD prophylaxis regimen. Subjects participating in the present add-on therapy study will contribute to the development of a drug which has the potential to become a treatment option for them and others in the future.

CONFIDENTIAL Page 48 of 108

### 2 STUDY OBJECTIVES

The primary objective of this study is to assess the efficacy of PRO 140 compared to placebo as an add-on therapy to standard GVHD prophylaxis in adult patients with AML or MDS undergoing allogeneic HCT.

The secondary objective of this study is to assess safety and tolerability of PRO 140 compared to placebo as an add-on therapy to standard GVHD prophylaxis in adult patients with AML or MDS undergoing allogeneic HCT.

# **Study Endpoints**

Primary Efficacy Endpoint

Incidence of Grade II, Grade III or Grade IV acute GVHD by Day-100

# Secondary Efficacy Endpoints

- Incidence of severe and life-threatening (Grade III and Grade IV) acute GVHD by Day 100
- Incidence of organ-specific acute GVHD by Day-100
- Donor engraftment evaluated by T-cell and myeloid chimerism in peripheral blood
- Neutrophil and platelet count recovery
- Changes in ECOG performance score
- GVHD-free survival (GFS)

# Safety Assessments

- Tolerability of repeated subcutaneous administration of PRO 140 as assessed by study participants (using Visual Analogue Scale) and by investigator-evaluation of injection site reactions
- Frequency of treatment emergent adverse events and serious adverse events
- AML or MDS relapse rate by Day-100
- Changes and shifts in laboratory measurements over time
- Changes in Electrocardiogram (ECG) parameters over time

CONFIDENTIAL Page 49 of 108

### 3 STUDY DESIGN

# 3.1 STUDY CENTER(S)

Approximately up to 20 centers in the United States will enroll patients in this study.

### 3.2 STUDY POPULATION

This study will recruit 60 subjects with Acute Myeloid Leukemia (AML) or Myelodysplastic Syndromes (MDS) undergoing allogeneic stem-cell transplantation.

#### 3.3 ELIGIBILITY CRITERIA

#### 3.3.1 Inclusion Criteria

Subjects must meet all of the following criteria to be included in the study:

- 1. Patients diagnosed with AML or MDS per below:
  - Patients with a history of histologically or pathologically confirmed diagnosis of AML and < 5% blasts in the peripheral blood or bone marrow (per bone marrow aspiration and/or biopsy within 6 weeks prior to screening) scheduled to undergo allogeneic stem-cell transplantation
  - Patients with a histologically or pathologically confirmed diagnosis of MDS with
     10% blasts in the bone marrow (per bone marrow aspiration and/or biopsy within 6 weeks prior to screening) scheduled to undergo allogeneic stem-cell transplantation
- 2. Eastern Cooperative Oncology Group (ECOG) performance status score  $\leq 2$
- 3. Patients must have normal organ function as defined below:
  - Myeloablative allogeneic HCT:
    - Males and females, age  $\ge 18$  and  $\le 65$  years of age
    - Total bilirubin  $\leq$  2 mg/dL (except in patients with Gilbert's Syndrome)
    - AST/ALT  $\leq$  3 times institutional upper limit of normal (except in patients with leukemic infiltration of liver)
    - Serum creatinine  $\leq 2 \text{ mg/dL}$  and creatinine clearance  $\geq 60 \text{ ml/hr}$
    - Diffusing capacity of the lung for carbon monoxide (DLCO) > 50% predicted with no symptomatic pulmonary disease
    - Cardiac ejection fraction ≥ 50%. If between 40-49% a cardiology consult is required

CONFIDENTIAL Page 50 of 108

[figure not shown]
- Clinically normal resting 12-lead ECG at screening visit or, if abnormal, considered not clinically significant by the PI
- 4. Patients must have a reasonable expectation of  $\geq 6$  months survival
- 5. The donor-recipient HLA match criteria required for participation in this protocol are not research subjects in this study and they must meet criteria as National Marrow Donor Program (NMDP) donors. Procedures for selection of donors and stem cell dose will follow FDA requirements for Blood Products (21 CFR 640) and Human Cellular and Tissue Based Products (21 CFR 1271). The standard institutional practices for stem cell transplants also will be followed. The donors are:
  - o HLA-Identical Sibling (6/6): Minimal typing necessary is serologic typing for class I (AB) and molecular typing for class II (DRB1)
  - Matched Unrelated Donor (8/8): Molecular identity at HLA A, B, C and DRB1 by high-resolution typing
  - o Matched Related and Unrelated Donor (7/8): high-resolution molecular typing at the following loci is required: HLA A, B, C and DRB1
- 6. Both male and female patients and their partners of childbearing potential must agree to use appropriate birth control methods (birth control pills, barriers, or abstinence) throughout the study duration (excluding women who are not of childbearing potential and men who have been sterilized). Females of childbearing potential must have a negative serum pregnancy test at Screening visit and negative urine pregnancy test prior to receiving the first dose of study drug.
- 7. Patients must understand and voluntarily sign an informed consent form

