## 3.3.2 Exclusion Criteria

Subjects meeting any of the following criteria will be excluded from the study:

- 1. Patients not expected to be available for follow-up for at least 114 days after transplant
- 2. Patients who have received prior allogeneic stem cell-transplantation
- 3. Patients who receive post-transplant high dose cyclophosphamide
- 4. Patients with active central nervous system (CNS) involvement by malignant cells
- 5. Patients receiving other investigational drugs for GVHD. Co-enrollment in other clinical trials that do not include experimental GVHD therapies is allowed

CONFIDENTIAL Page 51 of 108

[figure not shown]

- 6. Prior use of any experimental or approved CCR5 modulator including maraviroc and PRO 140
- 7. Patients with uncontrolled bacterial, viral or fungal infections including diagnosis of acute viral hepatitis (defined as any active infection with hepatitis A or a new diagnosis of hepatitis B or C within 24 weeks of dosing)
- 8. Currently active second malignancy other than non-melanoma skin cancers
- 9. Presence of fluid collection (ascites, pleural or pericardial effusion) that interferes with methotrexate clearance or makes methotrexate use contraindicated
- 10. Patients who are HIV positive
- 11. Females who are pregnant, lactating, or breastfeeding, or who plan to become pregnant during the study
- 12. Subjects on chronic steroid therapy > 5 mg/day within 2 weeks of screening except for inhaled, nasal, or topical steroids
- 13. Any other clinical condition that, in the Investigator's judgment, would potentially compromise study compliance or the ability to evaluate safety/efficacy

[figure not shown]
CONFIDENTIAL Page 52 of 108

Figure 3-1: Study Flow Diagram

CONFIDENTIAL Page 53 of 108

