## 7.11.2 Biochemistry

• Biochemistry profile includes assessment of:

Hepatic function indicators: total and direct bilirubin, alkaline phosphatase (ALP), aspartate aminotransferase (AST), alanine aminotransferase (ALT), total protein, Lactate dehydrogenase (LDH)

Renal function indicators: Blood Urea Nitrogen (BUN), creatinine

Electrolytes: sodium, potassium, chloride, calcium and bicarbonate

Other: glucose (random), cholesterol (total)

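### The creatinine-clearance limit is printed as 60 ml/hr (1 mL/min), so that half of the renal criterion screens out no one and renal eligibility rests on serum creatinine of at most 2 mg/dL alone

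*Protocol*

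**What the plan says.** Protocol section 3.3.1, criterion 3, opens with "Patients must have normal organ function as defined below". Its renal item has two parts joined by a conjunction, "Serum creatinine $\leq 2 \text{ mg/dL}$ and creatinine clearance", and the second part sets the lower limit: "creatinine clearance $\geq 60 \text{ ml/hr", that is, at least 60 ml/hr. The Inclusion Criteria in the synopsis print the same item with the same unit. No other section of the protocol gives a clearance limit in a different unit, and the SAP does not restate the criterion.

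The protocol does not say whether clearance is measured or calculated, or by what formula. The renal tests in section 7.11.2 are "Blood Urea Nitrogen (BUN), creatinine". The screening procedures in section 4.1.1 include that biochemistry panel, but list no clearance measurement.

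**The concern.** A requirement joined to the creatinine cap by a conjunction should add something to it. As printed, the clearance requirement adds nothing, although it sits under a heading that promises normal organ function.

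Two things are at stake.

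- **Who is enrolled.** Serum creatinine is the only numerical renal limit left, and the clearance that corresponds to a given creatinine varies with age, sex and weight. Patients with reduced clearance can meet the criterion and enter a trial that uses myeloablative conditioning (section 7.19.1) and defines standard prophylaxis as tacrolimus plus methotrexate (section 7.14).
- **Whether sites apply the same rule.** Up to 20 centers are to enrol 60 subjects (sections 3.1 and 3.2). One site may follow the printed unit while another assumes a misprint. They would then differ on whom they enrol and on what counts as an entrance-criteria deviation (SAP section 8.1.2). If such a deviation is classed as a major violation, per-protocol membership is affected as well (SAP section 6.2).

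**Working it through.** The plan derives no figure here that could be reproduced. The check is a unit conversion, followed by an illustration of what the two-part item admits.

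**Inputs from the protocol (section 3.3.1):** clearance limit 60 ml/hr; serum creatinine cap 2 mg/dL; age range, "Males and females, age $\ge 18$ and $\le 65$ years of age".

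**Assumptions, not in the documents:** the Cockcroft-Gault formula and body weights of 45 to 90 kg.

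**Step 1. Convert the unit.** 60 ml/hr ÷ 60 min/hr = 1.0 mL/min.

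**Step 2. Clearance at the creatinine cap.** Clearance (mL/min) = (140 − age) × weight ÷ (72 × creatinine), multiplied by 0.85 for women. With creatinine = 2.0 mg/dL the divisor is 144.

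| Patient | Calculation | Clearance (mL/min) |
|---|---|---|
| Man, 18 y, 90 kg | 122 × 90 ÷ 144 | 76 |
| Man, 18 y, 70 kg | 122 × 70 ÷ 144 | 59 |
| Man, 40 y, 70 kg | 100 × 70 ÷ 144 | 49 |
| Man, 65 y, 70 kg | 75 × 70 ÷ 144 | 36 |
| Woman, 65 y, 70 kg | 0.85 × 75 × 70 ÷ 144 | 31 |
| Man, 65 y, 50 kg | 75 × 50 ÷ 144 | 26 |
| Woman, 65 y, 50 kg | 0.85 × 75 × 50 ÷ 144 | 22 |
| Woman, 65 y, 45 kg | 0.85 × 75 × 45 ÷ 144 | 20 |

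The range is about 20 to 76 mL/min, or 20 to 76 times the printed limit. The full grid crossed ages 18, 40 and 65, weights 45, 50, 60, 70 and 90 kg, and both sexes, giving 30 combinations. Of these, 7 fall below 30 mL/min, 20 lie between 30 and 60, and 3 exceed 60. All 7 below 30 are at age 65 with weight of 60 kg or less, or are women aged 40 weighing 50 kg or less. These are counts of grid cells, not expected proportions of patients.

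**Step 3. Creatinine needed to fail the printed limit.** Setting clearance to 1 mL/min gives creatinine = (140 − age) × weight ÷ 72, times 0.85 for women.

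- Woman, 65 y, 45 kg: 0.85 × 75 × 45 ÷ 72 = 40 mg/dL.
- Man, 18 y, 90 kg: 122 × 90 ÷ 72 = about 152 mg/dL.

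Both are far above the 2 mg/dL cap, so under the assumed formula anyone who would fail the clearance part has already failed the creatinine part.

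**Step 4. How far two readings can diverge.** Suppose a site took the printed number as per minute. The limit would become 60 × 60 = 3,600 ml/hr, 60 times the printed one. Clearance would reach 60 mL/min at the following creatinine values:

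- Man, 18 y, 70 kg: 122 × 70 ÷ (72 × 60) = 1.98 mg/dL.
- Man, 65 y, 70 kg: 75 × 70 ÷ (72 × 60) = 1.22 mg/dL.
- Woman, 65 y, 50 kg: 0.85 × 75 × 50 ÷ (72 × 60) = 0.74 mg/dL.

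A 65-year-old, 70 kg man with creatinine between 1.22 and 2.0 mg/dL would be eligible under the text and ineligible under that reading. This shows only how much hangs on the unit. It is not evidence of which unit was meant.

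**The case against.** The strongest reply is that the renal item still works through its other half. Anyone with creatinine above 2 mg/dL is excluded whatever the clearance limit says. This stands. A reader might infer from the unit that the whole criterion excludes nobody, or that severe renal impairment in general passes as normal. The text does not support either: only the clearance part is empty, and under the assumptions above values below 30 mL/min at the cap arise mainly in older or lighter patients.

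Three further inferences also go too far.

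- **Exclusion 9.** It refers to fluid that "interferes with methotrexate clearance or makes methotrexate use contraindicated", and one might take it as proof of what the renal limit was meant to achieve. It covers fluid collections only and says nothing about renal function.
- **The DMC triggers in section 9.1.10.** The toxicity trigger counts only events that the investigator judges at least possibly related to study drug, so toxicity from poor baseline renal function would not count unless misattributed. The trigger of more than 20 percent mortality by day +100 is not limited in that way and could be affected, but it leads to DMC review rather than automatic stopping.
- **Bias.** Allocation is randomized and double-blind, so a loose entry rule applies to both arms and does not in itself bias the comparison. No sample-size, power or error-rate figure depends on this criterion.

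There are also safeguards. Exclusion 13 covers "Any other clinical condition that, in the Investigator's judgment, would potentially compromise study" compliance or the evaluation of safety and efficacy. Criterion 4 requires an expected survival of at least six months, and section 7.14 leaves dose modification of tacrolimus and methotrexate to institutional standards. These reduce the chance that a clearly impaired patient is enrolled without thought. They are matters of judgment and differ between sites, so they do not replace a numerical limit.

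The identical printing in two places makes a text-extraction error unlikely.

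**Conclusion.** The point holds for the clearance limit. It is wrong as written in both places: 1 mL/min does not screen anyone who meets the creatinine cap and does not fit the aim of normal organ function. Renal eligibility therefore rests on serum creatinine of at most 2 mg/dL, which under the assumptions admits patients at the cap with clearance of about 20 to 76 mL/min.

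The unit conversion is certain. The range depends on Cockcroft-Gault, on weights of 45 to 90 kg and on a creatinine exactly at the cap; lower creatinine gives higher clearance. The number of patients affected cannot be estimated from the documents.

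A reader might also conclude that the limit must have been meant per minute. The documents do not establish that. They show neither the intended unit nor whether clearance is to be measured or calculated, and this review does not say which limit is right.

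**What to change.** The sponsor should:

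1. confirm the intended unit and limit for creatinine clearance and reconcile it with the stated requirement of normal organ function;
2. correct the synopsis and section 3.3.1 together, in one amendment;
3. state how clearance is obtained, whether measured or calculated, and by which method;
4. notify all sites, so that they apply the same rule and record entrance-criteria deviations against the same limit.

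The text change is small, but it alters eligibility and so needs IRB approval before use (sections 11.3 and 13.1). There may be a few more screen failures at sites that had applied the printed unit. No statistical analysis needs to change.

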## 3.3.2 Exclusion Criteria

Subjects meeting any of the following criteria will be excluded from the study:

- 1. Patients not expected to be available for follow-up for at least 114 days after transplant
- 2. Patients who have received prior allogeneic stem cell-transplantation
- 3. Patients who receive post-transplant high dose cyclophosphamide
- 4. Patients with active central nervous system (CNS) involvement by malignant cells
- 5. Patients receiving other investigational drugs for GVHD. Co-enrollment in other clinical trials that do not include experimental GVHD therapies is allowed

CONFIDENTIAL Page 51 of 108

[figure not shown]

- 6. Prior use of any experimental or approved CCR5 modulator including maraviroc and PRO 140
- 7. Patients with uncontrolled bacterial, viral or fungal infections including diagnosis of acute viral hepatitis (defined as any active infection with hepatitis A or a new diagnosis of hepatitis B or C within 24 weeks of dosing)
- 8. Currently active second malignancy other than non-melanoma skin cancers
- 9. Presence of fluid collection (ascites, pleural or pericardial effusion) that interferes with methotrexate clearance or makes methotrexate use contraindicated
- 10. Patients who are HIV positive
- 11. Females who are pregnant, lactating, or breastfeeding, or who plan to become pregnant during the study
- 12. Subjects on chronic steroid therapy > 5 mg/day within 2 weeks of screening except for inhaled, nasal, or topical steroids
- 13. Any other clinical condition that, in the Investigator's judgment, would potentially compromise study compliance or the ability to evaluate safety/efficacy

[figure not shown]
CONFIDENTIAL Page 52 of 108

Figure 3-1: Study Flow Diagram

CONFIDENTIAL Page 53 of 108

### 4 STUDY SCHEDULE

This research study is divided into three study phases:

- (1) Screening Phase (Screening to T1 Visit) begins with signing of Informed Consent and lasts up to 4 weeks (28 days).
- (2) Treatment Phase (up to 14 weeks ± allowed windows). Eligible subjects will be randomized and receive up to 11 study treatments (PRO 140 or placebo), given on Day -3 or Day -2 prior to stem cell infusion, on the day of stem cell infusion (Day 0), and then weekly for 30 days (at Week 1, Week 2, Week 3 and Week 4) after which it will be administered every two weeks for up to 98 days (at Week 6, Week 8, Week 10, Week 12 and Week 14).
- (3) Follow-Up Phase (up to one year). Subjects who have completed the Treatment phase or who have withdrawn from the study will be followed-up at 2 weeks after the last treatment visit and one year after first treatment visit.

Procedures to be performed during each of these study phases are described below and provided as a Schedule of Assessments in Table 4-1.

CONFIDENTIAL Page 54 of 108

Table 4-1: Schedule of Assessments

iis	iV bəlub	əųəsu	n						×	×	×	×		×	×				
p Phase le year)	Follow-up Visit 2	52	Day 365±14							×						X			
Follow-Up Phase (up to one year)	Follow-up Visit 1	16	Day 112±3							X	X		X	×	X	X			
	T11	14	Day 98±3						×	×	×		X	×	X		X	×	X
	T10	12	Day 84±3							×				×	X	X			
	T9	01	Day 70±3							×	×		X	×	X				
	T8	œ	Day 56±3						X	X				×	X	X			
Phase	T7	9	Day 42±3							X	X			×	X		X	X	X
Treatment Phase (14 weeks)	9L	4	Day 28±3							X			X	×	X	X			
Tre	TS	e	Day 21±3											X					
	T4	2	Day 14±3							×	×			×	Х				
	T3	-	Day 7±3											×					
	T2		Day 0						×	×				×					
	T.1		Day -3/- 2			×	×			×	×		X	×	X	X			[6]X
Screening Phase (up to 4 weeks)	Screening Visit	Up to -4 weeks	Up to -28 days		×	×	×	×	×	×	×	X	X	×	X	X	X	×	
				Protocol Section	Section 7.1	Section 7.2	Section 7.4	Section 7.3	Section 7.6	Section 7.9	Section 7.10	Section 7.9	Section 7.7	Section 7.11.1	Section 7.11.2	Section 7.11.3	Section 7.11.8	Section 7.11.7	Section 7.11.6
Study Phase	Visit	Weeks	Days	Procedures	Informed Consent 	Eligibility Evaluation 	Medical History 	Subject Demographic	Physical Examination	Vital Signs 	ECOG performance score	Height and Weight	ECG	Complete Blood Count (CBC) 	Serum Biochemistry 	ЬРК	Urinalysis 	Serum Pregnancy Test 	Anti-idiotypic antibodies to PRO 140

Page 55 of 108 CONFIDENTIAL

tisi	iV bəlub	əyəsu	n							X	X		X	×
Follow-Up Phase (up to one year)	Follow-up Visit 2	52	Day 365±14				X						X	X
Follow-Up Phas (up to one year)	Follow-up Visit 1	16	Day 112±3							X			X	X
	T111	14	Day 98±3			×	×		×	X	X	X	X	X
	T10	12	Day 84±3						×	X	X	X	X	X
	L19	10	Day 70±3						×	X	X	X	X	X
	T8	8	Day 56±3			×	×		×	X	X	X	X	X
Phase ks)	41	9	Day 42±3						X	X	X	X	X	X
Treatment Phase (14 weeks)	9L	4	Day 28±3			X	X		X	X	X	X	X	X
Tr	TS	3	Day 21±3						X	X	X	X	X	X
	T4	2	Day 14±3			X			X	X	X	X	X	Х
	Т3	1	Day 7±3						×	X	X	X	X	X
	T2		Day 0			×			×	X 	×	×	X	×
	TI		Day -3/-					×	×		X		X 	X
Screening Phase (up to 4 weeks)	Screening Visit	Up to -4 weeks	Up to -28 days		×									X
				Protocol Section	Section 7.8	Section 7.11.4	Section 7.11.5	Section 7.12	Section 7.13	Section 7.17	Section 7.15	Section 7.16	Section 9.1	Section 7.5
Study Phase	Visit	Weeks	Days	Procedures	HIV rapid antigen test	Lymphocyte Phenotype Panel	T-cell and myeloid chimerism	Randomization	Administration of PRO 140 or Placebo	Grading GVHD – skin, gut, liver 	Injection Site Reaction Evaluation	Injection Site Pain Assessment (VAS) 	Adverse Events	Prior and Concomitant Meds

Informed consent must be obtained prior to patient participation in any protocol-related activities that are not part of routine care.

Initial evaluation of patient eligibility will be performed by Investigator.  $\overline{2}\overline{2}\overline{2}$ 

Medical history, past surgeries, disease history, history of substance abuse, social history will be recorded as Medical History up to the first randomized Treatment at Visit T1

4 5 9

Post treatment vital signs will be recorded (sitting blood pressure, heart rate, respiration rate, and temperature)
Hemoglobin, Hematocrit (HCT), Red Blood Cells (RBC), White Blood Cells (WBC) with total and differential count, Absolute Neutrophil Count (ANC) and platelets

Serum Biochemistry:

Hepatic function indicators: total and direct bilirubin, alkaline phosphatase (ALP), aspartate aminotransferase (AST), alanine aminotransferase (ALT), total

[figure not shown]

Version 3.0 Date: 17 Jun 2016

protein, Lactate dehydrogenase (LDH)

- Renal function indicators: Blood Urea Nitrogen (BUN), creatinine
  - Electrolytes: sodium, potassium, chloride, calcium and bicarbonate
    - Other: glucose (random), cholesterol (total)
- ONLY for women of childbearing potential Urine samples will be tested for color, appearance, specific gravity, pH, protein, glucose, occult blood, ketones, RBC, WBC, epithelial cells, bacteria, casts, crystals Anti-idiotypic antibodies to PRO 140 at visit T1 to be performed prior to dosing
- For GVHD diagnosis and grading refer to sections 7.17 and 7.18 After PRO 140 or Placebo dosing
- [7] [8] [9] [11] [12]
- Injection Site Pain Assessment (VAS) will be performed prior to study treatment administration beginning at visit T2 (to assess the average pain felt at the injection site since the last injection)

Page 57 of 108 CONFIDENTIAL

#### 4.1 SCREENING PHASE

### 4.1.1 Screening Visit

The subject (or Legally Acceptable Representative (LAR)) will sign and date the informed consent form (ICF) and Health Insurance Portability Accountability Act (HIPAA) authorization (according to site policy and practices) prior to any study-related procedures. A unique identification number (screening number) will be assigned to each subject who has provided written informed consent. The subject screening number will incorporate a two-digit Study Center number (01, 02 or 03....) and a three-digit numeric ID assigned in successive order of entering the study after signing the ICF at each center, beginning with 001 at each site (e.g. 01-001 or 02-001).

Subject Screening #: XX - YYY

XX=Study Center YYY=Subject Numeric ID

All study centers will be instructed to maintain the study-specific pre-screening, screening and enrollment logs at their sites. If a subject initially fails to meet inclusion/exclusion criteria and is later reconsidered for participation, the subject will be re-consented and assigned a new screening number at the time of re-screening. Subjects who fail their first screening attempt may be re-screened a maximum of once and may be enrolled if they are found to meet all inclusion and no exclusion criteria when re-screened.

Once the ICF has been signed, screening procedures and information will be obtained to confirm subject eligibility, including:

- 1. Medical history (section 7.4),
- 2. Subject demographics (section 7.3),
- 3. Physical examination (section 7.6),
- 4. Vital Signs (section 7.9),
- 5. Body Weight & Height measurements (section 7.9)
- 6. Eastern Cooperative Oncology Group (ECOG) performance status (section 7.10)
- 7. Prior and current medications review (section 7.5),
- 8. Electrocardiogram (ECG) (section 7.7)
- 9. Collection of Blood Specimens for:
  - o Complete Blood Count (CBC) w/diff (section 7.11.1)

CONFIDENTIAL Page 58 of 108

Version 3.0 Date: 17 Jun 2016

- o Biochemistry (section 7.11.2)
- Serum pregnancy test, for female subjects of childbearing potential (section 7.11.7). Childbearing potential is defined as someone who is not surgically sterile or is not more than one year past complete cessation of menstrual cycles.
- 10. Collection of Urine Specimen for Urinalysis (section 7.11.8)
- 11. HIV rapid antigen testing (section 7.8)

All screening information will be fully documented in the subject's medical records (i.e., source documents).

- For consented subjects who do not meet eligibility criteria, a Screen Failure electronic Case Report Form (eCRF) will be completed. The Screen Failure eCRF will contain the following details: the subject identification number, the date of ICF signature, demographic information, and the reason for screen failure. No additional information will be required for subjects who fail screening.
- For consented subjects who meet eligibility criteria, all required screening information will be transcribed onto the appropriate page of the eCRF.

Eligible subjects that are not enrolled within 28 days of Screening Visit will have screening lab assessments repeated to reconfirm eligibility.

